Drug treatment: the subject took a concomitant medication (either prescription or non-prescription) specifically for this AE
 OR existing concomitant medication dosage was modified as a result of this AE.

confidential information and ucb property

This document cannot be used to support any marketing application for an extension of the patent rights or variations thereof.

Hospitalization or prolongation of hospitalization	The subject was hospitalized for this AE or subject's stay in hospital was prolonged because of this AE.
Therapeutic or diagnostic procedure	Subject used other therapeutic measures (e.g. ice, heating pad, brace, cast, etc.) or subject underwent a diagnostic procedure (e.g., additional lab test, x-ray, etc.) for this AE.
Date of outcome:	Date (and time) the AE abated. If the AE consists of several signs and symptoms (syndrome), the sign or symptom with the longest duration determines the duration of the AE. If the AE is marked "ongoing", the outcome date should be blank.
Resolved	The AE is no longer present at any intensity - completely abated.
Resolved with sequelae	The AE is resolved but residual effects are still present.
Worsened	The AE is still present but at a heightened intensity. The rule of repetition of AE reporting should be applied.
Fatal	This AE caused or directly contributed to subject's death.
Ongoing	The AE is still present at the last contact with the subject.
Relationship to investigational product:	
None	only applicable when no investigational product was taken or when the subject is taking single-blind placebo, or when the AE can be ascribed with reasonable certainty to another cause.
Unlikely	there are good reasons to think that there is no relationship, e.g. the AE is a known adverse drug reaction of a concomitant medication.
Possible	equally valid arguments can be considered for or against an implication of the investigational product, e.g. the AE: 
 • follows a reasonable temporal sequence from the administration of the investigational product; • follows a known or expected response pattern to the investigational product; • but could readily have been produced by a number of other factors.

confidential information and ucb property

This document cannot be used to support any marketing application or variations thereof.

Probable

the relationship is likely, e.g. the AE:

- follows a reasonable temporal sequence from administration of the investigational product;

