- follows a known or expected response pattern to the investigational product;
- is confirmed by improvement on stopping or reducing the dosage of the investigational product;
- could not be reasonably explained by the known characteristics of the subject's clinical

Highly probable

there is a strong relationship, e.g. the AE:

- follows a reasonable temporal sequence from administration of the investigational product or in which the investigational product level has been established in body fluids or tissues;
- follows a known or expected response pattern to the investigational product;
- is confirmed by improvement on stopping or reducing the dosage of the investigational product, and reappearance of the AE on repeated exposure (rechallenge).

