4.8 Examination of subgroups

Selected summaries will be provided for the following subgroups as specified within each of the following sections:

- Two mappings of countries to regions are defined, 1 based on the classification requested by Food and Drug Administration (FDA), and 1 based on the regional classification for the CHMP (Committee for Medicinal Products for Human Use).

Countries will be mapped to geographic regions as follows for the FDA:

Geographic Region (FDA)	Country
North America	Canada, United States, Puerto Rico
Latin America	Brazil, Mexico
Western Europe	Austria, Belgium, Finland, France, Germany, Ireland, Italy, Netherlands, Norway, Réunion, Spain, Sweden, United Kingdom, Switzerland
Eastern Europe	Bulgaria, Czech Republic, Estonia, Latvia, Hungary, Lithuania, Poland, Romania, Russia, Serbia and Montenegro, Turkey, Ukraine
Asia/Pacific/Other	Australia, Hong Kong, India, Israel, Japan, Singapore, South Africa, Republic of Korea, Taiwan, Tunisia

Countries will be mapped to geographic regions as follows for the CHMP:

Geographic Region (CHMP)	Country
North America	Canada, United States, Puerto Rico
Latin America	Brazil, Mexico
Europe (European Union [EU] member states) *	Austria, Belgium, Bulgaria, Czech Republic, Estonia, Finland, France, Germany, Hungary, Ireland, Italy, Latvia, Lithuania, Netherlands, Norway, Poland, Réunion, Romania, Spain, Sweden, United Kingdom
Europe (non-EU member states)	Russia, Serbia and Montenegro, Switzerland, Turkey, Ukraine
Asia/Pacific/Other	Australia, Hong Kong, India, Israel, Japan, Singapore, South Africa, Republic of Korea, Taiwan, Tunisia

* EU member states plus Norway.

- Indication (Partial Onset Seizures, Primary Generalized Seizures, ULD)
- Randomized treatment in the previous study (placebo [PBO], BRV)

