5 STUDY POPULATION CHARACTERISTICS

5.1 Subject disposition

Due to differences in data format across studies, in order to facilitate summary of subject disposition, the reasons for discontinuation for individual studies will be collapsed as follows for summaries:

LTFU Category	CRF Reason
ADVERSE EVENT	ADVERSE EVENT
LACK OF EFFICACY	LACK OF EFFICACY
	LOSS OF EFFICACY
LOST TO FOLLOW-UP	LOST TO FOLLOW-UP
SUBJECT CHOICE	CONSENT WITHDRAWN
	WITHDRAWAL OF CONSENT FOR PERSONAL REASONS NOT RELATED TO AES
	WITHDRAWAL OF CONSENT FOR PERSONAL REASONS NOT RELATED TO AES OR LACK OF EFFICACY
OTHER	PROTOCOL VIOLATION
	OTHER REASON
	OTHER
MISSING	If subject discontinued the study and the termination CRF is not available

Only 1 primary reason for discontinuation should have been reported. In the event that more than 1 reason is specified in the clinical database, both reasons will be summarized and a

footnote will be added to the summary table to indicate that at least 1 subject is counted for multiple reasons for discontinuation.

An overall summary of disposition will be provided for all enrolled subjects (ie, all subjects who signed informed consent). The following will be summarized:

- The number of subjects in the Safety Analysis Set
- The number of subjects excluded from the Safety Analysis Set
- The number of subjects completed the study
- The number of subjects discontinued from the study, including the reason for discontinuation. If subject discontinued the study and the termination CRF is not available, the reason for discontinuation will be reported as “MISSING”.

Additionally, an overall summary of disposition will present the following for subjects in the Safety Analysis Set:

- The number of subjects completed the study
- The overall number of subjects discontinued and the number of subjects discontinued by primary reason for discontinuation. If subject discontinued the study and the termination CRF is not available, the reason for discontinuation will be reported as “MISSING”.

Overall subject disposition will also be summarized by geographic region and indication for the Safety Analysis Set.

The number of subjects within each geographic region and the number of subjects with each indication will be summarized for the Safety Analysis Set.

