11.2.2 General summaries of TEAEs

Pre-treatment AEs will be provided in a subject data listing; no summaries of pre-treatment AEs are planned.

An overall summary of AEs will provide the overall number of TEAEs and the numbers and percentages of subjects with at least 1 TEAE, with a TEAE that led to permanent discontinuation of study drug, with a drug-related TEAE, with a severe TEAE, with a treatment-emergent SAE, and with a drug-related treatment-emergent SAE. The number and percentage of subjects who died will also be summarized. This summary will be provided for all subjects in the Safety Analysis Set and also by subgroup for geographic region and indication.

The following summaries of TEAEs will be provided by MedDRA SOC and PT. All summaries are for the combined Evaluation, Down-Titration, and Post-Treatment Periods unless otherwise indicated.

Overall Incidence Summaries

- Incidence of TEAEs
- Incidence of TEAEs by 3-month time interval
- Incidence of TEAEs by study period (Evaluation, Down-Titration, Post-Treatment)
- Incidence of TEAEs for TEAEs occurring in at least 5% of subjects

- Incidence of TEAEs by 3-month time intervals for TEAEs occurring in at least 5% of subjects overall
- Incidence of non-serious TEAEs occurring in at least 5% of subjects

The incidence of TEAEs occurring in at least 5% of subjects will be summarized overall as noted above and also by subgroup for geographic region, indication, and randomized treatment from the previous double-blind study.

A subject is included in a 3-month interval if the subject was receiving BRV at any time during that interval based on their duration of exposure to BRV (eg, a subject with exposure for 91 days is included in the time interval for Months 1-3 and Months 4-6). Summaries of AEs by 3-month intervals will include all subjects who are classified into each time interval as defined above. TEAEs which had onset prior to or on the date of the last dose of BRV are included in summaries by 3-month time intervals.

Maximum Intensity and Causality

- Incidence of TEAEs by maximum intensity
- Incidence of drug-related TEAEs

Serious Adverse Events

- Incidence of treatment-emergent SAEs

Discontinuations due to TEAE

- Incidence of TEAEs leading to permanent discontinuation of study drug

TEAEs of interest

AEs of interest will be identified based on MedDRA search criteria, which are documented outside of the SAP. The following summaries will be provided for AEs of interest:

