- Incidence of TEAEs of interest
- Incidence of TEAEs of interest by 3-month time interval

For the summary by maximum intensity, each subject will be counted at most once per SOC or PT according to the maximum intensity of all AEs within that SOC or PT. Severe intensity will be assumed for AEs for which intensity is not specified.

Drug-related AEs are AEs for which the relationship to study drug is specified as Related or AEs for which relationship is not specified.

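### Does the SAP's *Related* label, absent from the protocol's five-level causality scale, leave the drug-related AE tables undefined?

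*SAP*

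**What the plan says.** SAP 11.2.2 gives the rule: "Drug-related AEs are AEs for which the relationship to study drug is specified as Related or AEs for which relationship is not specified". It applies the rule in two places. The overall AE summary counts subjects "with a drug-related TEAE, with a severe TEAE, with a treatment-emergent SAE, and with a drug-related treatment-emergent SAE", and is repeated by geographic region and indication. The list of tables by system organ class (SOC) and preferred term (PT) includes "Incidence of drug-related TEAEs".

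Protocol 12.3.2.2 tells investigators how to describe relationship to the investigational product and lists five ordered levels: None, Unlikely, Possible, Probable and Highly probable. Unlikely means that "there are good reasons to think that there is no relationship". Possible means that "equally valid arguments can be considered for or against an implication of the investigational product". Highly probable is introduced with "there is a strong relationship, e.g. the AE".

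Neither document states which of the five levels the SAP means by Related.

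**The concern.** A table specification should produce the same table in two programmers' hands. Here the SAP's key value does not appear on the protocol's scale. Taken as a literal text match, an AE graded Highly probable would be left out while an ungraded AE would be counted, which cannot be intended. Someone therefore has to supply a cut-point that is not written down, and different cuts could give different numbers of subjects with drug-related TEAEs and SAEs.

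The omission also looks out of character, because the SAP prints mappings elsewhere. For disposition, "the reasons for discontinuation for individual studies will be collapsed as follows for summaries", and similar tables exist for racial group and qualitative urinalysis. Long-term safety is the primary objective of a study with no control arm, so a reader might lean on investigator attribution more than usual.

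**Working it through.** There is no plan figure to reproduce, and neither document gives AE counts by causality level. The check sets the two texts side by side and counts what depends on the link.

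**1. What the data might hold.** The SAP rule acts on a recorded value. The protocol levels are guidance to investigators on describing an AE; they are not a database specification. The wording of None allows for a subject on single-blind placebo, which cannot occur in this open-label, single-arm study, so the text looks generic. Protocol 15.4 also says the CRF will be adapted as assessments change. Two cases remain:

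- The field holds Related/Not related. The SAP rule is then complete.
- The field holds the five levels. A cut is then needed.

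**2. Candidate cuts if the five levels were collected.**

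| Reading | Levels counted | Plausible? |
|---|---|---|
| Literal text match | 0 of 5 | No: drops Highly probable but counts missing |
| Highly probable only | 1 of 5 | No: drops Probable, which the protocol describes as a likely relationship |
| Probable and above | 2 of 5 | Arguable |
| Possible and above | 3 of 5 | Yes |
| Unlikely and above | 4 of 5 | No: contradicts the protocol's own definition of Unlikely |

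The live choice is 2 or 3 levels, that is, whether Possible counts. SAP 11.2.2 resolves missing data toward the worse outcome twice: missing relationship counts as drug-related, and missing intensity counts as severe. Counting an AE with no rating while leaving out one with evenly balanced arguments would be inconsistent, so 3 of 5 is the natural reading. For the drug-related TEAE row, the two cuts differ only by subjects who have a Possible TEAE and none rated higher or left unrated.

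**3. What depends on it.**

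- Overall AE summary: number of TEAEs; subjects with any TEAE, a TEAE leading to discontinuation, a drug-related TEAE, a severe TEAE, an SAE or a drug-related SAE; and deaths. That is 8 lines, of which 2 use causality.
- SOC/PT tables in SAP 11.2.2: 6 overall incidence + 2 intensity and causality + 1 SAE + 1 discontinuation + 2 AEs of interest = 12, of which 1 uses causality.
- Cells in the overall summary with one five-region mapping: (1 overall + 3 indications + 5 regions) × 2 rows = 18. In SAP 4.8, "Two mappings of countries to regions are defined", and three of the five regions are identical in both. Using both gives 1 + 3 + 5 + 2 = 11 distinct columns and 11 × 2 = 22 distinct cells. These counts show where the rule reaches; they do not show how far any rate would move.
- Primary safety variables (SAP 2.2.1.1): TEAE, withdrawal due to AE, SAE. Those using causality: 0 of 3.

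**The case for a change.** The best case for a change is that the protocol leaves statistical detail to the SAP, that the SAP either prints a mapping or says when a rule is held elsewhere (as for AED search terms and AEs of interest), and that here it does neither. Even a Related/Not related CRF field would leave the SAP and the protocol unreconciled on paper. One sentence would settle it with no new data.

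The textual part of that stands: the labels differ and nothing joins them. The comparison with other mappings is weaker than it looks. SAP 5.1 and 6.1 give inconsistent collection across studies as the reason for their tables, and SAP 13.3.3 says laboratories score urine differently. The absence of a causality table fits equally well with a field that its authors saw as already holding Related.

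The appeal to the primary objective does not carry far either. The protocol's own list of planned AE tables (Protocol 13.1.3) covers TEAEs, AEs leading to withdrawal and SAEs, and asks for no drug-related table. SAP 3.1 provides listings of source data and key derived variables, so recorded causality should be open to inspection whichever cut is used. A cut-point written in by a reviewer would also be a choice that no part of either document makes.

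**Conclusion.** No change to the plan is needed. This is missing detail that analysts would fill sensibly: they would use the recorded Related value if the CRF has one, or Possible and above if it holds the five levels. Calling the rows undefined goes too far, because the missing-value rule is explicit and the literal reading is one no analyst would apply.

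The reach is 2 of 8 overall summary lines and 1 of 12 SOC/PT tables, with 0 of 3 primary safety variables affected. All analyses are descriptive, with no hypothesis testing and no comparator, so no stated conclusion depends on the cut. A table footnote naming the values counted would be good practice, but the plan does not fail without it.

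This rests on two assumptions that the documents cannot confirm: what the CRF collected, and that analysts would carry the SAP's worst-case handling of missing causality over to Possible. The effect on drug-related rates is unknown.

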11.3 Clinical laboratory evaluations

Clinical laboratory parameters (blood chemistry, hematology, urinalysis) are assessed at all FEVs, YEVs, EDVs, and at FV, and may also be assessed at Unscheduled Visits.

For subjects entering the study from N01315, the clinical laboratory assessments will be provided in subject data listings only. The baseline assessment of these subjects will not be carried over from the previous studies.

11.3.1 Hematology and blood chemistry parameters

Observed values for each planned hematology and blood chemistry parameter will be summarized for Baseline, Study Entry, and each scheduled visit during the Evaluation Period for which laboratory parameters were assessed, Last Value, EDV, and FV. Change from Baseline will be summarized for all post-Baseline time points including EV. Only laboratory parameters planned per protocol will be summarized; results for laboratory parameters not planned per the protocol will only be provided in subject data listings.

The number and percentage of subjects with an on-treatment potentially clinically significant treatment-emergent (PCST) value, PCST low value, and PCST high value will be summarized. This summary will consider all assessments after the first dose of BRV and prior to or on the date of the last dose of BRV.

Additionally, the number and percentage of subjects with a PCST value, PCST low value, and PCST high value will be summarized for Baseline, Study Entry, each visit during the Evaluation Period for which laboratory parameters were scheduled to be assessed, EDV, Last Value, and FV. Percentages for each parameter and time point will be relative to the number of subjects with a value at that time point.

PCST criteria (Sections 13.3.1 and 13.3.2) are based on FDA Division of Neuropharmacologic Drug Products guidelines with some UCB-defined additions.

Creatinine clearance, when available from the central laboratory, will be provided in subject data listings only and will not be summarized.

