Treatment-emergent adverse events will be summarized by categories of total duration of exposure, period, and Medical Dictionary for Regulatory Activities (MedDRA[®]) Primary System Organ Class and Preferred Term in incidence tables. Separate tables will be provided, by categories of total duration of exposure, for AEs leading to withdrawal from the study and SAEs.

Laboratory values, vital signs, and weight will be summarized by period and visit. Possibly clinically significant treatment-emergent abnormalities for laboratory values, vital signs, and weight will be listed and summarized by period and visit. Electrocardiogram abnormalities, as well as physical and neurological abnormalities, will also be listed by period and visit.

Hospital anxiety and depression scales will be analyzed for the POS/PGS subpopulation only.

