13.3 PCST criteria

13.3.1 Hematology parameters

Parameter	UCB Conventional Units	SI Units	CF
Hematocrit	For 1 m to < 6 m: ≤ 25% For 6 m to < 2 y: ≤ 27% For 2 y to < 4 y: ≤ 29% For 4 y to < 12 y: ≤ 32% (Female[F]); ≤ 35% (Male [M]) For ≥ 12 y: ≤ 32% (F); ≤ 37% (M)	For 1 m to < 6 m: ≤ 0.25 For 6 m to < 2 y: ≤ 0.27 For 2 y to < 4 y: ≤ 0.29 For 4 y to < 12 y: ≤ 0.32 (F); ≤ 0.35 (M) For ≥ 12 y: ≤ 0.32 (F); ≤ 0.37 (M)	0.01
Hemoglobin	For < 6 m: ≤ 9.7 g/dL For 6 m to < 12 y: ≤ 10.0 g/dL For ≥ 12 y: ≤ 9.5 g/dL (F); ≤ 11.5 g/dL (M)	For < 6 m: ≤ 97 g/L For 6 m to < 12 y: ≤ 100 g/L For ≥ 12 y: ≤ 95 g/L (F); ≤ 115 g/L (M)	10
Platelets	≤ 75 x 10 ⁹ /L or ≥ 700 x 10 ⁹ /L	≤ 75 x 10 ⁹ /L or ≥ 700 x 10 ⁹ /L	Not applicable (N/A)
White Blood Cell (WBC)	For < 17 y: ≤ 3.0 x 10 ⁹ /L or ≥ 20 x 10 ⁹ /L; For ≥ 17 y: ≤ 2.8 x 10 ⁹ /L or ≥ 16 x 10 ⁹ /L;	For < 17 y: ≤ 3.0 x 10 ⁹ /L or ≥ 20 x 10 ⁹ /L; For ≥ 17 y: ≤ 2.8 x 10 ⁹ /L or ≥ 16 x 10 ⁹ /L;	N/A
Red Blood Cell (RBC)	For < 17 y: ≤ 2.5 x 10 ⁶ /mm ³ For ≥ 17 y: ≤ 2.0 x 10 ⁶ /mm ³ (F); ≤ 2.5 x 10 ⁶ /mm ³ (M)	For < 17 y: ≤ 2.5 x 10 ¹² /L For ≥ 17 y: ≤ 2.0 x 10 ¹² /L (F); ≤ 2.5 x 10 ¹² /L (M)	1
Eosinophils	≥ 10% or ≥ 0.7 x 10 ⁹ /L	≥ 0.10 or ≥ 0.7 x 10 ⁹ /L	0.01 or N/A
Neutrophils	≤ 15% or ≤ 1.0 x 10 ⁹ /L	≤ 0.15 or ≤ 1.0 x 10 ⁹ /L	0.01 or N/A
Basophils	≥ 5% or ≥ 0.4 x 10 ⁹ /L	≥ 0.05 or ≥ 0.4 x 10 ⁹ /L	0.01 or N/A
Monocytes	≥ 20% or ≥ 1.5 x 10 ⁹ /L	≥ 0.20 or ≥ 1.5 x 10 ⁹ /L	0.01 or N/A
Lymphocytes	For 1 m to < 6 m: ≤ 22% or ≥ 80% ≤ 2.1 x 10 ⁹ /L or ≥ 8.5 x 10 ⁹ /L For 6 m to < 2 y: ≤ 15% or ≥ 80% ≤ 1.5 x 10 ⁹ /L or ≥ 7.5 x 10 ⁹ /L For 2 y to < 12 y: ≤ 12% or ≥ 80% ≤ 1.0 x 10 ⁹ /L or ≥ 7.5 x 10 ⁹ /L For 12 y to < 17 y: ≤ 10% or ≥ 80% ≤ 0.5 x 10 ⁹ /L or ≥ 5.5 x 10 ⁹ /L For ≥ 17 y: ≤ 10% or ≥ 80% ≤ 0.5 x 10 ⁹ /L or ≥ 4.5 x 10 ⁹ /L	For 1 m to < 6 m: ≤ 0.22 or ≥ 0.80 ≤ 2.1 x 10 ⁹ /L or ≥ 8.5 x 10 ⁹ /L For 6 m to < 2 y: ≤ 0.15 or ≥ 0.80 ≤ 1.5 x 10 ⁹ /L or ≥ 7.5 x 10 ⁹ /L For 2 y to < 12 y: ≤ 0.12 or ≥ 0.80 ≤ 1.0 x 10 ⁹ /L or ≥ 7.5 x 10 ⁹ /L For 12 y to < 17 y: ≤ 0.10 or ≥ 0.80 ≤ 0.5 x 10 ⁹ /L or ≥ 5.5 x 10 ⁹ /L For ≥ 17 y: ≤ 0.10 or ≥ 0.80 ≤ 0.5 x 10 ⁹ /L or ≥ 4.5 x 10 ⁹ /L	0.01 N/A 0.01 N/A 0.01 N/A 0.01 N/A 0.01 N/A

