13.3.2 Blood chemistry parameters

Parameter	UCB Conventional Units	SI Units	CF
AST (SGOT)	≥ 3 times of ULN	≥ 3 times of ULN	N/A
ALT (SGPT)	≥ 3 times of ULN	≥ 3 times of ULN	N/A
ALP	For < 17 y: ≥ 2 times of ULN, if normal range adjusted to the age range; For ≥ 17 y: ≥ 3 times of ULN	For < 17 y: ≥ 2 times of ULN, if normal range adjusted to the age range; For ≥ 17 y: ≥ 3 times of ULN	N/A
GGT	≥ 3 times of ULN, if baseline value ≤ 3 times of ULN	≥ 3 times of ULN, if baseline value ≤ 3 times of ULN	N/A
BUN	≥ 30 mg/dL	≥ 10.71 mmol/L	0.357
Urea	≥ 60 mg/dL	≥ 10.02 mmol/L	0.167
Creatinine	For < 17 y: ≥ 1.5 mg/dL; For ≥ 17 y: ≥ 2.0 mg/dL	For < 17 y: ≥ 132.6 umol/L; For ≥ 17 y: ≥ 176.8 umol/L	88.4
Creatinine clearance (calc)	For < 12 y: < 70 ml/min (Schwartz) ^(a) For ≥ 12 y: < 70 ml/min (Cockcroft) ^(b)	For < 12 y: < 70 ml/min (Schwartz) ^(a) For ≥ 12 y: < 70 ml/min (Cockcroft) ^(b)	N/A
Total bilirubin	≥ 2.0 mg/dL	≥ 34.2 umol/L	17.1
Glucose	≤ 50 mg/dL or ≥ 180 mg/dL	≤ 2.775 mmol/L or ≥ 9.99 mmol/L	0.0555
Total Protein	For ≥ 1 m to < 6 m: ≤ 3.6 g/dL or ≥ 7.8 g/dL For ≥ 6 m to < 17 y: ≤ 4.7 g/dL or ≥ 9.5 g/dL For ≥ 17 y: ≤ 4.5 g/dL or ≥ 9.0 g/dL	For ≥ 1 m to < 6 m: ≤ 36 g/L or ≥ 78 g/L For ≥ 6 m to < 17 y: ≤ 47 g/L or ≥ 95 g/L For ≥ 17 y: ≤ 45 g/L or ≥ 90 g/L	10
Albumin	For < 17 y: ≤ 2.4 g/dL or ≥ 6.5 g/dL For ≥ 17 y: ≤ 2.5 g/dL or ≥ 6.5 g/dL	For < 17 y: ≤ 24 g/L or ≥ 65 g/L For ≥ 17 y: ≤ 25 g/L or ≥ 65 g/L	10
Globulin	For < 17 y: ≤ 1.2 g/dL or ≥ 5.0 g/dL For ≥ 17 y: ≤ 1.5 g/dL or ≥ 5.0 g/dL	For < 17 y: ≤ 12 g/L or ≥ 50 g/L For ≥ 17 y: ≤ 15 g/L or ≥ 50 g/L	10
Sodium	For < 17 y: ≤ 120 mEq/L or ≥ 155 mEq/L For ≥ 17 y: ≤ 115 mEq/L or ≥ 155 mEq/L	For < 17 y: ≤ 120 mmol/L or ≥ 155 mmol/L For ≥ 17 y: ≤ 115 mmol/L or ≥ 155 mmol/L	1
Potassium	For < 17 y: ≤ 3.0 mEq/L or ≥ 6.5 mEq/L For ≥ 17 y: ≤ 3.0 mEq/L or ≥ 5.8 mEq/L	For < 17 y: ≤ 3.0 mmol/L or ≥ 6.5 mmol/L For ≥ 17 y: ≤ 3.0 mmol/L or ≥ 5.8 mmol/L	1
Calcium	For < 17 y: ≤ 7 mg/dL or ≥ 11.5 mg/dL For ≥ 17 y: ≤ 7 mg/dL or ≥ 15.5 mg/dL	For < 17 y: ≤ 1.75 mmol/L or ≥ 2.875 mmol/L For ≥ 17 y: ≤ 1.75 mmol/L or ≥ 3.875 mmol/L	0.25

Uric Acid	For < 12 y: ≥ 8 mg/dL For ≥ 12 y: ≥ 8 mg/dL (F); ≥ 9.5 mg/dL (M)	For < 12 y: ≥ 475.84 umol/L For ≥ 12 y: ≥ 475.84 umol/L (F); ≥ 565.06 umol/L (M)	59.48
Cholesterol	≥ 300 mg/dL	≥ 7.77 mmol/L	0.0259
HDL	≤ 25 mg/dL	≤ 0.65 mmol/L	0.0259
LDL	≥ 200 mg/dL	≥ 5.18 mmol/L	0.0259
Triglycerides	≥ 300 mg/dL	≥ 3.42 mmol/L	0.0114

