13.3.3 Urinalysis

Qualitative urine parameters are generally reported by a descriptive score, which differs among laboratories. For data analysis purpose, a four-point scale is used. Five-point, six-point, or seven-point scales will be collapsed into a four-point scale first. A value is considered possibly clinically significant treatment emergent abnormal if an upward shift of at least 2 degrees from the baseline occurs under investigational treatment. To collapse the results in a five-point scale into a four-point scale, the lowest two positive results will be combined (see example below). For results reported with a scale of more than five-point, please consult your study physician for how to collapse into four-point scale.

Original Five-point Scale	Four-point Scale
Negative/None	Negative/None
Trace/Rare/Mild/A Few	Trace/1+/Rare/Mild/A Few
1+	
2+/Mod	2+/Mod
3+/Sev	3+/Sev

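### Apart from GGT, the hematology and chemistry criteria for treatment-emergent (PCST) values ignore Baseline, so pre-existing abnormalities seen again on treatment are counted as emergent

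*SAP*

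**What the plan says.** Protocol 13.1.3 states the aim: "Possibly clinically significant treatment-emergent abnormalities for laboratory values, vital signs, and weight will be listed and summarized by period and visit". It does not define treatment-emergent for a laboratory value.

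SAP 11.3.1 carries this out in two summaries. The first counts "subjects with an on-treatment potentially clinically significant treatment-emergent (PCST) value", also split into low and high. Its only stated restriction is timing: "This summary will consider all assessments after the first dose of BRV and prior to or on the date of the last dose". The second counts subjects "with a PCST value, PCST low value, and PCST high value will be summarized for Baseline, Study Entry" and later time points.

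The criteria are in the appendix. Every row of SAP 13.3.1 (hematology) is a fixed limit, some by age or sex. For hemoglobin from age 12, for example, it is at most 9.5 g/dL in women and 11.5 g/dL in men. SAP 13.3.2 (chemistry) uses fixed limits or multiples of ULN. One chemistry row, GGT, looks at Baseline: "≥ 3 times of ULN, if baseline value ≤ 3 times of ULN".

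The other criteria are built differently. Urinalysis (SAP 13.3.3) needs an "upward shift of at least 2 degrees from the baseline". In SAP 13.3.4, pulse and blood pressure need both a limit and a change from Baseline, and adult weight needs a change of at least 7% of Baseline.

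Baseline is the pretreatment value of the previous study (Protocol 13.1.3) and is defined separately for each laboratory parameter (SAP 3.3). First dose means the first dose in N01125 (SAP 3.2.1).

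**The concern.** A value is treatment-emergent when it was not there before treatment. For almost all hematology and chemistry rows the plan checks only that the value was seen during treatment. A subject with low hemoglobin before the previous study began, and low again at any N01125 visit, enters the count. The summary is then closer to on-treatment prevalence than to new onset.

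The study is single-arm and descriptive, so no control group shows how much abnormality would be present anyway. Each subject's own Baseline is the natural reference, and this summary does not use it. Laboratory tests are repeated at full and yearly visits, which gives a long-standing abnormality many chances to be counted. A reader who takes the label literally may credit brivaracetam with abnormalities that preceded it.

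**Working it through.** **1. How many rows are affected.** SAP 13.3.1 lists 10 hematology parameters and SAP 13.3.2 lists 21 chemistry parameters, 31 in all. GGT has a Baseline condition and the other 30 do not. The ALP wording about an age-adjusted normal range concerns the reference range, not Baseline.

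SAP 11.3.1 summarizes only parameters planned in the protocol and lists creatinine clearance without summarizing it. Against Protocol 10.2.16, six chemistry rows are not planned: BUN, globulin, cholesterol, HDL, LDL and triglycerides. That leaves 21 − 6 − 1 = 14 chemistry rows, 13 of them without a Baseline condition. All 10 hematology rows are planned. The affected total is 10 + 13 = 23 of 24 summarized rows.

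**2. Internal consistency.**

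| Criterion | Uses Baseline? | PCST tabulated at Baseline? |
|---|---|---|
| Hematology; chemistry except GGT | No | Yes |
| GGT | Yes | Yes |
| Urinalysis | Yes (shift) | Yes |
| Pulse, blood pressure, adult weight | Yes (change) | No, starts at Study Entry (SAP 11.4.1) |

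A pretreatment value cannot be treatment-emergent. The Baseline entry makes sense for the first row of the table only if PCST there means simply beyond the limit.

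**3. Size.** The documents give no rate to reproduce. Let *p* be the share of subjects beyond the limit at Baseline, *s* the chance that such a subject is beyond it again on treatment, and *q* the new-onset rate among the rest. All three are assumptions.

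Reported rate = *p s* + (1 − *p*) *q*. The rate sought is *q*. The excess is *p*(*s* − *q*), which cannot exceed *p*.

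With *s* = 80% and *q* = 2%:

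| *p* | Reported rate | Ratio to *q* |
|---|---|---|
| 0.1% | 0.0008 + 0.01998 = 2.08% | 1.04 |
| 0.2% | 0.0016 + 0.01996 = 2.16% | 1.08 |
| 1% | 0.008 + 0.0198 = 2.78% | 1.39 |
| 3% | 0.024 + 0.0194 = 4.34% | 2.17 |
| 5% | 0.040 + 0.019 = 5.90% | 2.95 |

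**4. In subjects.** SAP 2.4 gives 859 enrolled, including 6 from N01315 who are outside the Safety Analysis Set. The set is therefore at most 859 − 6 = 853.

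- With *p* = 1%, *s* = 90%, *q* = 1%: 853 × (0.009 + 0.0099) = 16.1 counted, of whom 853 × 0.0099 = 8.4 are new. About 48% of the count is pre-existing.
- With *p* from 0.5% to 5%, *s* from 50% to 90% and *q* from 1% to 3%, the pre-existing share runs from about 8% to 83%.
- With *p* = 0.1% and *s* = 80%, the pre-existing cases number 853 × 0.001 × 0.8 = 0.7, less than one subject.

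**The case against.** The strongest reply has five parts.

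- **The variable is not primary.** The primary safety variables are TEAEs, withdrawal due to AE, and SAEs (SAP 2.2.1.1). Laboratory tests are other safety variables (SAP 2.2.1.2). TEAEs have their own onset rule (SAP 11.2.1), and no hypothesis is tested. This stands, and it limits the weight of the point.
- **Baseline information is already shown.** SAP 11.3.1 plans observed values at Baseline and at each visit, change from Baseline, and PCST percentages at Baseline and Study Entry; listings give the source data. This helps, but only in part. Two marginal percentages do not show whether the same subjects are in both, and no laboratory shift table is planned.
- **PCST may be only a fixed name for threshold tables.** Tabulating it at Baseline even for urinalysis suggests so. Relabelling would then cure the wording, but the emergent abnormalities that the protocol asks for would still not be reported.
- **Many limits are extreme.** Examples are platelets at or below 75 × 10⁹/L and adult sodium at or below 115 mEq/L. Protocol 8.2 also excludes subjects whose laboratory values may affect their safety. Baseline prevalence may be well under 1% for such rows, and the excess then negligible. This stands.
- **A blunt exclusion would do harm.** Dropping everyone who met the same criterion at Baseline would hide a subject whose ALT rises further. In two-sided rows such as glucose it would also hide a move from low to high. This stands, and it shapes the fix.

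A reader might infer that the plan contradicts a protocol definition, or that it hides abnormalities. Neither is supported. The protocol gives no definition, and the error runs toward over-counting.

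**Conclusion.** The concern holds for the on-treatment PCST summary of the 23 protocol-planned hematology and chemistry parameters other than GGT. As written, abnormalities present at the pretreatment Baseline and seen again on treatment are counted as treatment-emergent, which is inconsistent with the SAP's other criteria.

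Rates may be too high; the documents do not show that they will be, or by how much. Under the assumed 80% persistence and 2% new onset, the ratio is 1.4 to 3.0 at a Baseline prevalence of 1% to 5%, and 1.04 at 0.1%. If new onset were much rarer than 2%, the ratio at low prevalence would be larger, but the excess would still be bounded by the Baseline prevalence.

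It is tempting to read this as a flaw in the primary safety evaluation, because long-term safety is the primary objective. The documents do not support that: no primary safety variable is derived from PCST values. The change is worth making because it corrects a mislabelled safety summary at little cost.

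One reservation applies. A stretch of the SAP appendix between the hematology and chemistry tables was not in the text available, so a hematology footnote cannot be ruled out. Nothing visible refers to one.

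**What to change.** In SAP 11.3.1 and 13.3.1–13.3.2:

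1. Count a value as PCST low (or high) only if the subject's Baseline did not meet the criterion in that same direction. Derive the overall PCST count from the two.
2. Use subjects who did not meet the criterion at Baseline as the denominator. Show subjects who did meet it, and subjects with no Baseline value, on separate lines.
3. Add a shift table from Baseline to the worst on-treatment value, so that worsening from an abnormal Baseline stays visible.
4. Relabel the Baseline column PCS, without treatment-emergent.

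Keep the previous study's pretreatment Baseline as the reference, so that abnormalities which arose on brivaracetam in that study are still counted. Those that arose there on placebo will be counted too; a footnote should say so.

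The cost is SAP wording, one programming condition, a few extra lines and one extra table per parameter. Baseline is already derived for each parameter, and no data collection changes.
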